#### 4.2.2. Secondary Endpoints

#### Safety:

- Change from baseline in PRA
- Change from baseline in hematology, coagulation, and clinical chemistry parameters

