# 9.2. Safety Analyses

Safety analyses will be performed on all patients who have an HAV implanted when the final patient enrolled reaches 12 months post-implant

Incidence of HAV aneurysm formation (true or pseudo), anastomotic bleeding or spontaneous rupture, HAV infection, HAV removal, and significant local inflammation at the HAV implantation site will be separately tabulated and listed.

Adverse events will be coded using Medical Dictionary for Regulatory Activities (MedDRA) terms. Adverse events will be listed and summarized by system organ class, preferred term, incidence, severity, and duration. HAV complications will be listed in terms of incidence, severity, and (where appropriate) time to onset and duration. Serious adverse events will be summarized separately. Any premature discontinuations due to adverse events and deaths will be listed and summarized.

Laboratory data, including PRA, will be listed and summarized using appropriate descriptive statistics at each visit and for the absolute change from baseline values for all post-surgery visits. The closest non-missing values prior to surgery on Day 1 will be used as baseline values.

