1.4 Objectives

1.4.1 Primary Objectives:

This is an open label Phase 2 study. There is no formal hypothesis testing.

Statistical Analysis Plan	
CLN-PRO-004	

Final Analysis 8/23

Safety:

• To evaluate the safety and tolerability of the Humacyte HAV in PAD patients undergoing femoro-popliteal bypass surgery

Efficacy:

- To determine the patency (primary, primary assisted and secondary) rate of the Humacyte HAV at Month 12
- To determine the incidence of hemodynamically significant stenosis (>70%) defined by duplex ultrasound, and the time to stenosis development

1.4.2 Secondary Objectives:

Safety:

- To assess changes in the panel reactive antibodies (PRA) response after HAV implantation
- To determine mechanical stability of the HAV based on freedom from aneurysmal degeneration on duplex ultrasound and computed tomography (CT) imaging
- To determine HAV durability in terms of freedom from need for HAV explanation or replacement due to infection, bleeding or conduit degeneration

Efficacy:

- To determine the patency of the HAV (primary, primary assisted and secondary) at Months 3, 6 and 9
- To determine the rates of interventions needed to maintain / restore patency in the HAV through Month 12
- To assess effect of HAV implantation on symptoms of PAD using the VascuQol instrument
- To assess effect of the HAV on ankle-brachial index (ABI)
- To assess effect of the HAV on 6 minute walk test

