5.4 Safety Laboratory Parameters

Clinical laboratory variables will be described using summary statistics for the actual values at each visit, as well as for the absolute change from baseline to each visit. The standard error of the mean (SEM) will be included in these tables.

The following laboratory parameters were determined and will be described for the corresponding visits:

Hematology (measured at screening and Month 6)

- Hemoglobin
- Hematocrit
- Red Blood Cells (RBC)
- Absolute Lymphocytes
- Absolute Monocytes
- Absolute Eosinophil
- Absolute Basophil
- White Blood Cells (WBC)
- Absolute Neutrophil Count

Clinical Blood Chemistry (measured at screening and Month 6)

- Sodium
- Potassium
- Calcium

Final Analysis 19/23

- Blood Urea Nitrogen (BUN)
- Total Bilirubin
- Creatinine
- Glucose (non-fasting)
- Albumin

Coagulation (measured at screening and Month 6)

- International Normalized Ratio (INR)
- Activated Partial Thromboplastin Time (aPTT)

Immunology (measured at screening and Month 6)

• PRA sample collection date will be listed.

Hematology, chemistry and coagulation values are quantitative. The findings (normal, abnormal clinically significant [CS], abnormal not clinically significant [NCS]) are available for each test and will be provided in the listings.

The laboratory values were provided by local laboratories and unit values are not consistent across sites. The values used for the table summary will be **conventional units** and will be calculated by a conversion method.

6 Adverse Events (AEs)

Adverse events that started before HAV implantation are collected and documented in the EDC as medical history.

Adverse events will be coded by MedDRA. Presentation of adverse events will be the number of entries, as well as the number and percentage of affected patients. Tabulations will show numbers of adverse events by system organ class (SOC), preferred term (PT), and severity.

Each documented adverse event per patient will be considered, i.e. if a patient experienced the same adverse event (identical adverse event description) more than once during study duration, all events will be counted.

To give an overview of all adverse events a frequency table will be prepared showing the following information (displaying number of patients, percentage of patients and number of events).

Overview table:

- any AEs
- any serious AEs (SAEs)

Final Analysis 20/23

any AEs leading to death as outcome

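### SAP 5.4 specifies only a listing of PRA sample dates, although protocol 9.2 requires PRA results and their change from baseline to be summarized

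*SAP*

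**What the plan says.** **Protocol.** Section 3.2 makes the PRA response after implantation a secondary safety objective, and section 4.2.2 turns it into a secondary safety endpoint, "Change from baseline in PRA". Section 7.3.1 schedules PRA at screening and Month 6 and has it assayed centrally, unlike the other laboratory tests, which are run at the hospitals. Section 2.5.1 names PRA as the way possible antibody formation will be assessed. Section 9.2 sets the analysis: "Laboratory data, including PRA, will be listed and summarized using appropriate descriptive statistics at each visit and for the absolute change from baseline values".

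**SAP version 2.0.** Section 1.4.2 repeats the objective ("To assess changes in the panel reactive antibodies (PRA) response after HAV implantation") and section 2.2 repeats the endpoint. Section 5.4 opens with a general statement, "Clinical laboratory variables will be described using summary statistics for the actual values at each visit", together with change from baseline. It then introduces its parameter list with "The following laboratory parameters were determined and will be described for the corresponding visits". The list has four headings: hematology, clinical chemistry, coagulation and immunology. The single entry under immunology is "PRA sample collection date will be listed".

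**The concern.** The endpoint is a change in a measured result, but the output specified for it is a calendar date. Sections 1.4.2 and 2.2 of the SAP keep PRA as an objective and an endpoint, and section 5.4 gives no analysis that would report it.

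If the tables and listings are built from section 5.4 as written, a named secondary safety endpoint could go unreported, and with it the protocol's stated means of looking for an antibody response to the vessel. The protocol draws on PRA findings from the earlier studies when it summarizes immunogenicity (sections 2.4.3, 2.4.5 and 2.4.8), so a reader of the study report will expect the corresponding result here.

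**Working it through.** The plan states no figure on this point, so the check compares text and counts entries.

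**1. Mentions of PRA in the available SAP version 2.0 text.** There are four: the abbreviation list, the objective (1.4.2), the endpoint (2.2) and the sample-date line (5.4). Outputs that name PRA and give a value, a summary or a change: 0. Outputs that name PRA and give a date: 1.

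**2. Required against specified.** With PRA measured at screening and Month 6, protocol 9.2 implies the following.

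| Output for PRA | Protocol 9.2 | SAP 5.4 immunology line |
|---|---|---|
| Listing of results | required | not specified |
| Summary at screening | required | not specified |
| Summary at Month 6 | required | not specified |
| Summary of change from baseline | required | not specified |
| Listing of sample date | not mentioned | specified |

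**3. Does the opening of SAP 5.4 cover PRA?** The immunology heading stands below that opening, so the text is ambiguous. Three features weigh against relying on it:

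- *The entries.* Hematology has 9, chemistry 8 and coagulation 2, so 9 + 8 + 2 = 19 entries name a measured parameter. Adding the one immunology entry gives 19 + 1 = 20. That entry alone names a date and carries its own output instruction.
- *The data type.* The sentence after the list reads "Hematology, chemistry and coagulation values are quantitative". Immunology is left out.
- *The source.* The section continues "The laboratory values were provided by local laboratories and unit values are not consistent across sites" and plans a unit conversion. PRA comes from a central laboratory under protocol 7.3.1, so this description does not fit it.

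**4. Do other SAP sections cover it?** Section 3.4 says listings will show the available study data. That could at most produce a listing of PRA results, and only if those results are in the study database, which the documents do not show. It does not give the summaries.

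**5. Coverage of the laboratory schedule.** Leaving out the screening-only tests (pregnancy test and HbA1c), protocol 7.3.1 has 5 hematology + 8 chemistry + 2 coagulation + 1 PRA = 16 entries measured at both time points. SAP 5.4 names a result variable for 4 + 8 + 2 + 0 = 14. The two without one are PRA and platelet count. The platelet omission is a separate, minor matter and adds nothing to the PRA argument.

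**6. Amount of data.** SAP 1.5 gives 15 recruited patients. With two samples each, at most 15 × 2 = 30 PRA results and 15 changes from baseline would be reported.

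**The case against.** The strongest reply is that the plan under-specifies PRA but does not contradict the protocol. SAP section 4 sets defaults: counts and percentages for categorical data, standard summary statistics for continuous data, and a rule for baseline. Section 2.2 names the PRA change as an endpoint. Endpoint plus default method plus baseline rule gives a route to a summary, and the immunology line does not say that results will be withheld. The SAP also presents itself as an elaboration of the protocol, so protocol 9.2 can be read as still in force.

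That route exists for a well-disposed reader, which is why the consequence is stated as possible and not certain. It still supplies no PRA variable and does not say whether the result is categorical or continuous, so the default cannot be applied without a further decision. The specific line on PRA points to something else.

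Two further points deserve weight. Protocol 7.5.1 has the screening PRA sample taken for later analysis, so the date line may simply describe what the sites record while results arrive separately. That may explain the wording, but it does not provide the analysis. Also, the text of SAP version 2.0 stops at the heading of section 9. Section 10, on changes from the protocol, appears in the contents only, and section 9 or an appendix could hold relevant detail. This limit stands. The superseded SAP version 1.0 had the same date-only line and declared no changes from the protocol, but that does not show what section 10 of version 2.0 says.

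The objection that the stakes are small is correct, and it bounds the importance of the point.

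**Conclusion.** The point holds. In the available text of SAP version 2.0 the stated PRA output does not meet protocol 9.2 and cannot deliver the endpoint named in SAP 2.2: none of the four outputs that the protocol implies is specified for PRA.

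This should be corrected, but its reach is narrow. It concerns a secondary safety endpoint with a single post-baseline time point and at most 15 patients. The study is descriptive and tests no hypothesis, and no primary endpoint, error rate or sample size is affected. Confidence is medium, because the conclusion assumes that the unavailable parts of the SAP neither specify PRA results nor declare a departure.

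**What to change.** Replace the immunology line in SAP 5.4 with wording such as: *Central-laboratory PRA results at screening and Month 6 will be listed and summarized descriptively, with absolute change from baseline and the number of patients with paired samples.* Name the PRA result variable and say whether it is treated as continuous or categorical. The count of paired samples goes beyond protocol 9.2; it is suggested because with so few patients the reader needs the denominator for the change.

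If PRA results are not to be analyzed under this SAP, state and justify the departure from protocol 9.2 in the section on changes from the protocol.

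Separately, add platelet count to the hematology list, since protocol 7.3.1 measures it at both time points.

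The cost is a few lines of SAP text, a few outputs and possibly a data transfer from the central laboratory. No new visits or samples are needed beyond those already in the protocol.

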7.1 Other Long-Term Follow-Up Variables

Study duration will be evaluated calculating the number of days being in the trial:

Total Study Duration = Date of Last Visit Available – Date of Day 1 + 1

Descriptive measures will be presented for the total study duration. Individual patient's study duration will be listed.

7.2 Missing Values

Imputations of partial dates are used for the following: determination of study day/time of onset and duration of an AE; definitions of prior and concomitant medications; time to loss of patency; time to first stenosis; day/time of onset and duration of HAV complications. Imputations are made using a conservative approach, which aims to maximize the duration of AEs and HAV complications and minimize the time to loss of patency and time to first stenosis.

Date imputation method for AEs, prior/concomitant medications, and HAV complications

- Partial start dates
 - Missing time the minimum possible onset time will be calculated and presented

Statistical Analysis Plan	
CLN-PRO-004	

in DD:HH:MM format

- Missing day impute the 1st of the month. For AEs and HAV complications, if the month is the same month as the HAV implantation, then impute the day of the implant
- Missing day and month impute as January 1st. For AEs and HAV complications, if the year is the same year as the HAV implantation, then impute as the day of the implant
- Partial end dates
 - Missing time the maximum possible onset time will be calculated and presented in DD:HH:MM format
 - Missing day impute the last day of the month
 - Missing day and month impute as December 31st

Date imputation method for calculating time to loss of patency and time to first stenosis

- Partial patency status or stenosis status dates
 - Missing time the minimum possible onset time will be calculated and presented in DD:HH:MM format
 - Missing day impute the 1st of the month. If the month is the same month as the HAV implantation, then impute the day of the implant
 - Missing day and month impute as January 1st. If the year is the same year as the HAV implantation, then impute as the day of the implant

8 Data Base Closure and Data Review

A data base closure (soft lock) will be performed prior to the DRM and to the analysis. All parameters will be checked, as specified in the data validation plan, and all queries resolved before data base closure and analysis.

The data review will be conducted prior to final data base closure and can be done via a telephone conference or in writing. During the DRM it is to review and define patient's primary, primary assisted and secondary patency outcome (yes/no) and patient's time to loss of patency (primary, primary assisted and secondary). Additionally, adverse events of graft complications (aneurysm formation, anastomotic bleeding or rupture, graft infection and irritation/inflammation at the graft implantation site) will be identified.

For the data review meeting, ARG will provide patient data listings to the Sponsor, containing following information:

Statistical Analysis Plan	Final Analysis
CLN-PRO-004	22/23

- Any data on patient patency (primary, primary assisted, secondary) response classification (yes/ no) concerning the primary efficacy parameter and the secondary efficacy parameter on patency, as well as any data needed to define patients date of HAV failure and date of loss of patency
- Adverse event data (HAV complications)

The final decision regarding the patency outcomes and date of HAV failure/ loss of patency will be documented within a meeting minutes document. The Sponsor will review the document and verify the decision by signing the document.

The final data base closure (hard lock) will be performed afterwards.

9 Miscellaneous

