## 2.4.3. CLN-PRO-V002 Study Results (24 M)

Recruitment began in October 2013 and was completed in June 2014 with 20 patients implanted. Thirteen patients completed the 2 year follow up visit. Of the seven patients terminating the study early, three died and four were withdrawn after occlusion of the HAV. None of the deaths were considered related to the investigational device or procedure.

Kaplan-Meier analyses in which deaths were censored revealed primary, primary assisted, and secondary patency probability rates of 79.2%, 79.0%, and 89.5% at Week 26, 63.3%, 63.2%, and 84.2% at Month 12, 63.3%, 63.2%, and 79.0% at Month 18, and 58.1%, 57.9%, and 73.7% at Month 24.

Six patients (30%) required at least 1 graft intervention to maintain or restore HAV patency during the study. Four patients required 1 intervention and 1 patient each required 3 and 4 interventions. Most interventions successfully restored patency. However, in 1 patient the graft patency could not be restored and the HAV was replaced with an alternative bypass graft. Two patients, who had previously undergone successful interventions, developed a recurrent thrombosis which was not treated and the HAV was left occluded. Two patients experienced HAV thrombosis with no or minimal symptoms and refused interventions on the HAV.

Confidential

All 20 patients experienced AEs (a total of 92 events). Thirty-one of these events in 13 patients were considered serious. The most frequent AEs reported included graft thrombosis (35% of patients), anastomotic stenosis (20% of patients), lymphocele (20% of patients), and local swelling (15% of patient). Those serious adverse events (SAEs) reported by at least 2 patients were graft thrombosis (6 patients, 30%) and anastomotic stenosis (2 patients, 10%).

No patient showed an increase in PRA levels. Two patients had a significant (>2-fold) increase from baseline in IgG levels. One of these patients experienced a thrombosis of the HAV between 3 and 6 months after implantation, while the other patient has had no HAV-related AEs and continues to have primary patency. Neither patient has had any evidence of dilatation or structural degeneration of the HAV.

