# 6.4. Implantation of the Humacyte human acellular vessel (HAV)

The Humacyte HAV is implanted using standard vascular surgical techniques similar to placement of standard peripheral vascular prostheses (see study manual for details).

Tunneling of the HAV must be performed using a sheathed tunneler. During tunneling, the HAV should be handled by pulling on the Dacron cuff (see study manual for details)

After placement, HAV patency and integrity are checked by pressurizing the HAV. Prior to completion of surgery angiography is performed to confirm adequacy of the HAV anastomoses, HAV patency and peripheral runoff. The surgical site is closed using standard techniques.

Implantation of the HAV will be undertaken by qualified vascular surgeons experienced in peripheral arterial bypass surgery.

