4.4.4 Other Efficacy Variables

High Resolution Ultrasound

Doppler ultrasound (HAV patency) high resolution ultrasound data will be listed.

Time to loss of patency

Time after first implantation of HAV until loss of patency (primary, primary assisted and secondary) will be separately presented in tables using descriptive statistics. The time to loss of patency will be verified during the DRM using all data from the CRF including the information used for patency rates at each visit and information on any AEs and consequent interventions.

Patients discontinued early with the HAV still patent, will be censored at that timepoint.

The median times (or the lower quartile – in case the median is unable to be estimated) will be presented together with the respective 95% CIs using Kaplan-Meier estimates. In case of small numbers of events these analyses may be skipped.

For the 1-year interim analysis, time to loss of patency will be reviewed for the first 12 months, and rates of 3, 6, and 12 months will be presented. For the final analysis, time to loss of patency will be reviewed for the entire study and rates of 3, 6, 12, 24, 36, 48, and 60 months will be presented.

Focused vascular assessment exam will be listed.

Angiography and Endothelium-dependent, flow-mediated vasodilation data will be listed.

5 Safety Analysis

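### SAP 7.2 can date a loss of patency or a first stenosis before examinations that showed the HAV free of that event

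*SAP*

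**What the plan says.** SAP 7.2 gives a date rule for calculating time to loss of patency and time to first stenosis:

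- Day missing: the 1st of the month, except that "if the month is the same month as the HAV implantation, then impute the day of the implant".
- Day and month missing: "Missing day and month impute as January 1st", except that "if the year is the same year as the HAV implantation, then impute as the day of the implant". This exception appears in the AE rule and again in the patency and stenosis rule.

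The section calls the approach conservative and says that it aims to "minimize the time to loss of patency and time to first stenosis". It does not mention the last examination at which the HAV was patent or unstenosed. For AEs and HAV complications, a partial end date becomes the last day of the month or 31 December, with no limit at death, study exit or data cut.

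Two other sections bear on this. SAP 4.4.4 states: "The time to loss of patency will be verified during the DRM using all data from the CRF". SAP section 8 has the DRM define each patient's patency outcome and time to loss before hard lock: "The final decision regarding the patency outcomes and date of HAV failure/ loss of patency will be documented within a meeting minutes document". The sponsor signs those minutes.

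**The concern.** The trial records when the HAV was seen to be working. Protocol 6.4 states: "Prior to completion of surgery angiography is performed to confirm adequacy of the HAV anastomoses, HAV patency and peripheral runoff". Protocol 7.4.2 then schedules clinical duplex at Day 29, at Months 3, 6, 9 and 12, and six-monthly to Month 54. A rule bounded only by implantation can return a date that these records exclude, even the day on which patency was confirmed. The earliest date compatible with the data is the day after the last event-free assessment. An earlier date goes beyond conservatism and conflicts with recorded observations.

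The affected results are the Kaplan-Meier curves (SAP 4.4.1), the time-to-loss summaries and landmark rates (SAP 4.4.4), and time to first stenosis (SAP 4.4.1), which serves a primary efficacy objective. On the safety side, imputed AE and HAV-complication durations can run past the end of observation.

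**Working it through.** The plan gives no figure on this point to reproduce. The check applies the SAP 7.2 rule literally.

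**Inputs from the documents.** Imputation rule: SAP 7.2. Scan schedule: Protocol 7.4.2. Patients recruited: 15 (SAP 1.5). Study day = date − implant date + 1, the convention SAP 4.4.1 uses for first stenosis.

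**Assumed for illustration.** Implant dates, loss dates, and that every scan before the loss showed the HAV free of the event.

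**Dated examples.** The floor is the day after the last event-free scan before the loss.

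| | Implant | True loss | Recorded as | Rule gives | Event-free scans on or after that date | With floor |
|---|---|---|---|---|---|---|
| A | 1 Feb 2018 | 1 Dec 2018, day 304 | 2018 | day 1 | Day 29, Months 3, 6, 9 | day 275 |
| B | 1 Jul 2017 | 1 Sep 2018, day 428 | 2018 | 1 Jan 2018, day 185 | Months 6, 9, 12 | day 367 |
| C | 15 Jul 2017 | 25 Jul 2018, day 376 | Jul 2018 | 1 Jul 2018, day 352 | Month 12 | day 367 |

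In A the shift is 304 − 1 = 303 days, so the Kaplan-Meier estimates at 3 and 6 months count a loss that had not yet happened. In B and C a loss after Month 12 is counted in the 12-month estimate.

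**Grid.** Implants from October 2016 to September 2019 (assumed from the planned 4Q 2016 start and 36-month accrual), with a loss on each of days 2 to 366.

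- Year-only date: the imputed date falls on or before an event-free scan in 81% of cases. The maximum shift is 364 days and the mean is 122.
- Only the day missing: 16% of cases, maximum shift 30 days (31st to 1st).
- Year-only with the floor: maximum shift 91 days, mean 37.

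These percentages describe the rule on a uniform grid. They do not say how often partial dates occur.

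**Landmark rates.** Before censoring, one patient is 1/15 = 6.7 points. For example, 10/15 = 66.7% becomes 9/15 = 60.0%. For scale, the exact 95% interval for 10/15 is 38.4% to 88.2%.

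**Time to first stenosis.** Only patients with a stenosis contribute. With k contributors, a 303-day error moves the mean by 303/k: 101 days if k = 3, and 61 days if k = 5 (k assumed).

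**End dates.** If a patient exits on 1 January and an AE end date is known only by year, the rule gives 31 December: 365 − 1 = 364 days after exit in a non-leap year.

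**Which scans can contradict a date.** Under SAP 4.4.1, primary patency ends at any intervention and primary assisted patency ends at thrombosis, while secondary patency survives a successful procedure. A patent scan after treatment therefore does not contradict an earlier primary or assisted loss, nor does an unstenosed scan after treatment contradict an earlier first stenosis. Take implant 1 Feb 2018, a patent Month 3 scan on 1 May (day 90), thrombosis treated on 1 Jun (day 121) and dated only 2018, then patent scans through Month 12 (1 Feb 2019, day 366). SAP 7.2 gives day 1. A floor at the last patent scan of any kind gives day 367, which is outside the recorded year and turns a true first-year failure into a success. A floor at the last event-free assessment before the first evidence gives day 91.

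**The case against.** The strongest reply is the DRM. With 15 patients, a Day 1 loss followed by patent scans would probably be noticed, because SAP 4.4.4 and section 8 have time to loss reviewed against all CRF data. A wrong date is therefore possible but not automatic. The reply does not close the gap: the SAP does not say whether imputation comes before or after the DRM, or whether the DRM may replace an imputed date. The section 8 list covers patency and graft complications but not time to first stenosis. The trial is open-label and the sponsor signs the decision, so a later date is better set by a written rule than case by case.

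Year-only dates should also be uncommon. Occlusion is an event of special interest (Protocol 8.4), reportable within 24 hours of the site learning of it (8.5.6), and queries are resolved before soft lock (SAP section 8). That stands, although the 24 hours run from awareness rather than onset, and stenosis is not on the special-interest list.

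Three stronger readings are tempting, and the documents do not support them:

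- *The tabulated Month 3, 6, 9 and 12 rates would flip.* SAP 4.4.1 bases these on a yes/no assignment verified at the DRM with ultrasound among the sources, and SAP 7.2 does not list them among the uses of imputed dates.
- *The rule invents failures.* The failure is real. It is misplaced only between the imputed and the true date.
- *The earlier PAD study shows that partial dates are common.* Protocol 2.4.3 says: "Two patients experienced HAV thrombosis with no or minimal symptoms and refused interventions on the HAV". It says nothing about missing dates, and an unknown biological onset is not the same as a year-only record.

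**Conclusion.** The point holds in limited form. As written, SAP 7.2 can produce loss-of-patency and first-stenosis dates that the trial's own earlier examinations rule out, and end dates after observation stopped. That is a rule giving a wrong answer, not merely missing detail. The 12-month error needs both day and month missing. One affected patient moves a Kaplan-Meier landmark rate by about 6.7 points before censoring, which is small against the imprecision at N = 15 but avoidable.

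The direction is declared in advance and works against the product. All results are exploratory and no hypothesis is tested. The sizes rest on illustrative dates, and the documents do not say how many partial dates exist, so the realised effect may be nil.

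**What to change.** In SAP 7.2:

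1. Impute the event as the later of the current rule date and the day after the last assessment that showed the HAV free of that specific event, using only assessments before the first documented evidence of it (finding, AE report or intervention).
2. Keep the result within the known month or year and no later than that first evidence.
3. Do not use patent or unstenosed scans obtained after an intervention or re-established patency to move primary patency, primary assisted patency or first stenosis later.
4. Apply the rule at or before the DRM, for first stenosis as well as patency, and list every imputed date.
5. Cap imputed AE and HAV-complication end dates at the earliest of death, study exit and data cut.

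The cost is a few sentences and minor programming, using assessments already scheduled. The downside is slightly later, less conservative event dates.
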